3.1.6 Participation Criteria

- 1. Healthy volunteered individuals between 19 and 29 years old.
- 2. Individuals with a refraction power of less than -6.00 spherical diopters and astigmatism power of less than -1.00 cylindrical diopters.
- 3. Experienced contact lens wearers. (Participants are asked to lay off contact lenses for at least 2 weeks before the clinical trial starts (McKernan et al., 2014))

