3.1.9 Study Protocol

Participants for this study will be recruited from among UKM undergraduate students at the Kuala Lumpur Campus based on the inclusion and exclusion criteria. Recruitment of volunteers will be conducted through advertisement. Simple random sampling will be used for participant selection, with those meeting the inclusion criteria being eligible for the study, while those meeting the exclusion criteria will be dismissed.

Before the commencement of the clinical trial, all participants will be provided with a consent form to review. The study will take place at the UKM Optometry Clinic, [name], Kuala Lumpur, Malaysia.

Participants will be required to attend the UKM Optometry Clinic for three sessions, each lasting 8 hours, during which they will wear FDA hydrogel contact lenses (groups I, II, III, IV, Va and Vb). Each lens will be placed on one eye only. Hence, the study will involve three wearing sessions, with the first session focusing on groups I and II FDA contact lenses, the second session on groups III and IV FDA contact lenses, and the third session on hydrogel silicone contact lenses Va and Vb. A 2-week rest period will be provided between each session. The complete study procedure is outlined as follows:

Care for Contact Lenses Leaflet.

Ensuring proper hygiene and technique is crucial to prevent eye health complications while wearing contact lenses. Subjects will receive thorough guidance on essential practices, including: maintaining hygiene care, correctly utilizing contact lens solution, applying and removing contact lenses, and adhering to permissible actions during wear. Additionally, subjects will be provided with a hotline for any inquiries or emergencies arising during contact lens use. Furthermore, they will receive a pamphlet titled "Soft Contact Lens Instructions" available at the UKM KL Optometry Clinic.

[figure not shown]

Figure 1 & 2. Soft contact lens use instructions

Pre-Assessment

A pre-assessment will precede the contact lens application during the initial session. The parameters measured will include these three tests: a) assessment of tear quantity using the Schirmer Test, b) evaluation of tear quality with the NIBUT Test, and c) examination of corneal staining using the Efron Grading Scale. These same tests will be conducted after the contact lenses have been worn for 8 hours and subsequently removed.

a) Tear Quantity Assessment (Schirmer Test)

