Figure 3. Grading Scale Based on 5 Corneal Zones

i. Contact lens application

The placement of group I FDA contact lenses will occur on one side of the subject's eye, while group II FDA contact lenses will be positioned on the opposite side, with the positioning being randomized and unknown to the subjects. Researchers will delicately insert the contact lenses, providing clear instructions and precautions to the subjects regarding their wear. Subjects will be advised to remain near the UKM KL Campus throughout the contact lens application and return to the UKM Optometry Clinic after 8 hours for lens removal. Additionally, subjects will be instructed to promptly notify the researcher of any discomfort, pain, or unforeseen issues related to the wearing of contact lenses.

ii. Post-Wear Assessment

The researcher will remove the contact lenses from the subject's eyes. Subsequently, a postwearing examination of the contact lenses will be conducted. This examination mirrors the preuse assessment and includes a) evaluating tear quantity using the Schirmer Test, b) assessing tear quality with the NIBUT Test, and c) grading corneal staining based on the Efron Grading Scale. Following the removal of contact lenses, subjects will be required to complete the Contact Lens Discomfort Index (CLDI) questionnaire twice at each appointment: once for the right eye and once for the left eye. This allows for the measurement of comfort levels separately for each eye.

d) Contact Lens Discomfort Index Questionaires (CLDI)

The CLDI questionnaire will be employed to evaluate the comfort level during the usage of Group I and II FDA contact lenses. This questionnaire's selection of questions is rooted in the Contact Lens Dry Eyes Questionnaire (CLDEQ)-8. Known for its robustness and reliability, the CLDI questionnaire is specifically crafted to gauge comfort levels associated with contact lens wear (Arroyo-del Arroyo et al., 2022).

English version of the contact lens discomfort index (CLDI)

The Contact Lens Discomfort Index (CLDI) questionnaire is an easy instrument to measure the level of discomfort with the contact lenses.

Note: questions highlighted in grey correspond to the subscale score.

- Please, answer the following questions.
- 1. Since you have been wearing this type of contact lens, have you always worn them the same number of hours per day?
 - I currently use them more than previously (0)

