 - I use them the same amount as previously (1) I use them fewer hours per day than I previously did because I prefer to or because it was recommended to me (1)
 - I use them fewer hours per day due to dryness and/or discomfort (2)
- 2. Do you wear these contacts as many hours as you wish/need to?
 - Yes (0)
 - □ No (1)
- 3. Do you USUALLY wear contact lenses while using electronic devices/video display terminals?
 - □ No (respond to question 4.1) (0)
 - □ Yes (respond to question 4.2) (0)

- 4.1 If you do NOT use your contact lenses when using electronic devices/video display terminals, what is the reason? (you can select multiple responses)
 - Because I don't feel like it (0)
 - Because I don't see well or my eyes become red (0) Because they bother me or I notice dryness (1)
- 4.2 If you DO use contact lenses while using electronic devices/video display terminals, do you USUALLY notice discomfort with them?
 - No (0)
 - No (0)
 Yes (1)
- 5. Do you USUALLY notice problems with these contact lenses when in dry environments (air conditioning or heat), with low humidity or in the wind?
 - No (0)Yes (1)
- 6. Answer the following question by checking the box that best represents your response (only check one box per symptom). During a typical day in the past week, have you experienced any of the following symptoms?

	No, I have not experienced it (0)		rienced it only while contact lenses (1)	Yes, I experienced it both with and without contact lenses (2)				
Dryness								
Discomfort								
During a typical day in the past week, have you experienced any of the following symptoms both with and without contact lenses on? (you can select multiple options)		 8. Describe the level of discomfort right b removing your contact lenses. No discomfort (0) Somewhat uncomfortable (1) 						
 Red eyes (1) Itching (1) 				ortable (2) comfortable (3)				
 Poor vision (1) Watery eyes (1) 		 Describe your overall satisfaction with the use o these contact lenses. 						
None (0)			 Very satisfied Not satisfied 					

Figure 4. Contact Lens Discomfort Index (CLDI) Questionnaire

[figure not shown]
i. Rest Period

[figure not shown]
A "washout period," also known as a rest period, lasting for two weeks will be provided to the subjects to prevent any unauthorized observations.

ii. Second and Third Appointments

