3.1.10 Flow Chart

3.1.11 Data Analysis

The forthcoming study will employ IBM SPSS Statistics Version 27 for data analysis. The normality of the data will be assessed utilizing the Shapiro-Wilk test. Subsequently, the distribution of the data will be examined accordingly.

Utilize the Paired t-test for normally distributed data or the Wilcoxon signed-rank test for non-normally distributed data to assess the disparities in tear quality and quantity before and after
 Employ the Paired t-test for normally distributed data or the Wilcoxon signed-rank test for non-normally distributed data to compare the mean quality and quantity of tears between FDA contact lens application groups I and II, groups III and IV, as well as silicone hydrogel materials A and B.

iii. Employ the Paired t-test for normally distributed data or the Wilcoxon signed-rank test for non-normally distributed data to assess the comfort levels associated with the application of FDA contact lenses within groups I and II, groups III and IV, as well as silicone hydrogel materials A and B.

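### The per-eye CLDI total is a poor measure of comfort after one 8-hour wear, because Q1 to Q7 ask about past-week symptoms, usual habits or wearing hours

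*Protocol*

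**What the plan says.** **Exposure.** Protocol section 3.1.9 plans "three sessions, each lasting 8 hours, during which they will wear FDA hydrogel contact lenses", with a different lens type in each eye. The researcher inserts the lenses, and subjects "return to the UKM Optometry Clinic after 8 hours for lens removal". The protocol therefore sets the wearing time, and it is the same for both eyes.

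**Before each session.** Section 3.1.6 states: "Participants are asked to lay off contact lenses for at least 2 weeks before the clinical trial starts". Section 3.1.9 adds: "A 2-week rest period will be provided between each session". It also calls this interval a washout.

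**Instrument.** After lens removal, subjects complete the CLDI "questionnaire twice at each appointment: once for the right eye and once for the left eye". The form is reproduced in section 3.1.9 (Figure 4). Q1 begins: "Since you have been wearing this type of contact lens, have you always worn them the same number of hours per day". Q6 and Q7 both begin: "During a typical day in the past week, have you experienced any of the following symptoms". No instruction limits the answers to the session or to one eye.

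**Analysis.** Section 3.1.11 item iii uses a paired t-test or Wilcoxon signed-rank test "to assess the comfort levels associated with the application of FDA contact lenses within groups I and II, groups III and IV", and likewise for the two silicone hydrogel materials. It does not say whether the CLDI total, its subscale or single items are compared.

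**The concern.** Comfort appears in the study title, the research question and specific objective iii, and the CLDI is its only measure. The planned comparison is between two lenses worn at the same time by one person on one day. An item can inform that comparison only if it can be answered for that day, that lens and that eye. Most of the printed items are framed for someone who has worn one lens type for some time.

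If the total is analysed, a finding of no comfort difference would be hard to interpret. It could mean that the lenses are alike, or that the questions could not tell them apart. The research hypothesis in section 2.4 is one of no difference, so the ambiguity matters. A later analysis plan can choose which answers to use, but it cannot change the time frame in which they were given.

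**Working it through.** The protocol gives no figure to reproduce here, so the check sets each printed item against the exposure. Maximum points are those printed on the form.

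| Item | Frame | Max points | Fit to one 8-hour wear, per eye |
|---|---|---|---|
| Q1 | Change in daily wearing hours with this lens type | 2 | No history after one wear |
| Q2 | Hours as wished or needed | 1 | Hours set by protocol, equal for both eyes |
| Q3 | Usual lens wear with screens | 0 | Habit of the person; only routes to Q4 |
| Q4 | Reason for not wearing lenses with screens, or usual discomfort with them | 1 | Nothing is yet usual for this lens |
| Q5 | Usual problems in dry surroundings | 1 | As Q4 |
| Q6 | Past week: dryness, discomfort (0 to 2 each) | 4 | Session is one day of the week |
| Q7 | Past week: four symptoms, with and without lenses | 4 | As Q6, and not lens-specific |
| Q8 | Discomfort just before removal | 3 | Fits |
| Q9 | Overall satisfaction | not legible | Fits |

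**Share of the score.**
- Q1 to Q7: 2 + 1 + 0 + 1 + 1 + 4 + 4 = 13 points.
- With Q8: 13 + 3 = 16 legible points.
- Q9 assumed to be worth 1, 2 or 3 points: the total is 17, 18 or 19. The share of Q1 to Q7 is 13/17 = 76%, 13/18 = 72% or 13/19 = 68%.
- Past-week items alone (Q6 and Q7, 8 points): 8/17 = 47% down to 8/19 = 42%.
- Q8 and Q9 together: 4/17 = 24% up to 6/19 = 32%.

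**Recall window.** The session is 1 day of 7, or 8/168 = 4.8% of the hours. The rest of that week is meant to be lens-free. This is explicit before session 1 and inferred from the rest or washout period before sessions 2 and 3.

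**Scoring of Q6.** A symptom felt only while wearing lenses scores 1; one felt with and without lenses scores 2. Dryness brought on by the study lens thus earns fewer points than background dryness.

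**Effect on the paired difference.** Write the total difference as D(Q1–Q7) + D(Q8, Q9).
- If a subject answers Q1 to Q7 identically for both eyes, D(Q1–Q7) = 0 and the total carries exactly the Q8 and Q9 difference.
- If answers are arbitrary per eye, D(Q1–Q7) is noise with some SD s, and the SD of the total difference rises.

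**Illustration of the second route.** None of these inputs except n is in the documents. Assume a true Q8 difference of 0.5 with paired SD 0.7, no Q9 contribution, n = 16 (the count before the dropout allowance in section 3.1.4), a two-sided 5% paired t-test, and no lens signal in Q1 to Q7. The SD of the total difference is √(0.49 + s²).

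| s | SD of difference | Power |
|---|---|---|
| 0 | 0.70 | 76% |
| 0.5 | 0.86 | 59% |
| 1.0 | 1.22 | 34% |
| 1.5 | 1.66 | 20% |

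The table shows the direction of the effect. It does not measure the size of the loss in this trial.

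**The case against.** Several points on the other side are sound.

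- **The past week includes the wear day.** A reader might infer that Q6 and Q7 cover a week without any study lens. They do not: the form is completed after removal at the same appointment. If the rest period is lens-free, Q6's option for symptoms felt only with lenses even points to the study lenses. Q6 is badly framed but not empty.
- **Identical answers do no harm to the contrast.** A reader might infer that both routes push the result towards no difference. Only arbitrary per-eye answers do so. Identical answers cancel and leave Q8 and Q9 intact.
- **Q4.2 and Q5 may carry some signal.** Subjects stay near campus for 8 hours and may meet screens and air conditioning. Treating these items as pure noise is an assumption.
- **The scored set is open.** The form mentions a subscale marked in grey, which cannot be seen in the text available, and the choice of score may be left to an analysis plan. But the protocol selects no subscale, and no choice of score changes what Q1 to Q7 asked.
- **The instrument is published.** The protocol calls it robust and reliable. It would go too far to say that the validation covers habitual wear only, because that source is not at hand. What can be said is that the protocol cites no support for single-session, per-eye use. The Q6 scoring belongs to the published form and is not a protocol error; it matters here because of the use made of it.

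None of this makes Q1 to Q7 suitable for comparing two lenses worn once, side by side.

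**Conclusion.** The point holds for the CLDI score, not for every item. Seven of the nine numbered items have a frame that does not match a single fixed 8-hour wear per eye. They hold 13 of 16 legible points, or about 68% to 76% of the total if Q9 is worth 1 to 3 points. Dividing by 16 would give 81% (and 50% for the past-week items), but that leaves out Q9, which is answerable, so the lower range is the fair one.

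The total would be labelled lens comfort although most of it does not describe that lens on that day. The loss of power is real only so far as subjects give arbitrary per-eye answers, and the documents do not let us size it. Q8 and Q9 are already collected per eye, so a usable comparison is within reach. The change should be made, but it is a cheap improvement rather than a fatal flaw: comfort is one of three outcome domains, and the tear and staining outcomes are unaffected.

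**What to change.** In sections 3.1.9 and 3.1.11 item iii:

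1. Base the I vs II, III vs IV and Va vs Vb comfort comparisons on Q8, answered separately for each eye at the 8-hour visit, with Q9 in support.
2. Report the full CLDI total descriptively only.
3. Optionally, re-anchor Q4.2 to Q7 to today's 8 hours in this eye, and leave Q1 to Q3 out of the per-eye score.

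**Cost.** Steps 1 and 2 change only the analysis text. Step 3 also changes the form and must be done before subjects complete it. No visit, procedure or staff time is added.

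**Downside.** A single item or a reworded form departs from the published full score, and the protocol cites no support for single-session, per-eye use of either version. Q8 has four levels (0 to 3), so paired differences are whole numbers from −3 to 3 and ties are likely. Q8 alone also leaves out dryness, which the re-anchored Q6 would keep.

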3.1.10 Flow Chart

3.1.11 Data Analysis

The forthcoming study will employ IBM SPSS Statistics Version 27 for data analysis. The normality of the data will be assessed utilizing the Shapiro-Wilk test. Subsequently, the distribution of the data will be examined accordingly.

Utilize the Paired t-test for normally distributed data or the Wilcoxon signed-rank test for non-normally distributed data to assess the disparities in tear quality and quantity before and after
 Employ the Paired t-test for normally distributed data or the Wilcoxon signed-rank test for non-normally distributed data to compare the mean quality and quantity of tears between FDA contact lens application groups I and II, groups III and IV, as well as silicone hydrogel materials A and B.

iii. Employ the Paired t-test for normally distributed data or the Wilcoxon signed-rank test for non-normally distributed data to assess the comfort levels associated with the application of FDA contact lenses within groups I and II, groups III and IV, as well as silicone hydrogel materials A and B.

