2.4 Research Hypothesis

Among UKM undergraduate students at the Kuala Lumpur Campus, there was no significant disparity observed in tear assessment, corneal staining, and comfort levels before and after one day (8 hours) of wearing Group I, II, III, IV, and silicone hydrogel contact lenses.

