2.5 Conceptual framework

Figure 1 illustrates the conceptual framework for assessing tear quantity, corneal staining, and comfort levels during the wear of FDA contact lenses Group I, II, III, IV, and V materials.

2.6 **Objectives**

2.6.1 General Objectives:

The objective is to examine the impact of FDA contact lenses Group I, II, III, IV, and silicone hydrogel on tear assessment, corneal staining, and comfort levels among undergraduate students at UKM Kuala Lumpur Campus.

2.6.2 Specific Objectives:

i. Assessing tear quantity, corneal staining, and comfort levels before and after 8 hours of wearing FDA contact lenses Group I, II, III, IV, and silicone hydrogel.

ii. Contrasting tear evaluation and corneal staining pre- and post-8-hour application of FDA contact lenses Group I, II, III, IV, and silicone hydrogel.

iii. Comparing comfort levels pre- and post-8-hour wear among FDA contact lenses Group I,II, III, IV, and silicone hydrogel (Va and Vb).

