To assess tear quantity, the Schirmer test will be employed using a 5mm x 30mm Schirmer strip. The strip will be positioned in the temporal area of the subject's lower eyelid. The subject will be instructed to look upwards and blink naturally for 5 minutes, after which the Schirmer strip will be removed. The length of the wet portion of the strip will be measured and documented. Three readings will be obtained in millimeters (mm), and the average reading will be calculated for data analysis (Kallarackal et al., 2002).

b) Tear Quality Assessment (NIBUT Test)

The assessment of tear quality was conducted using the Non-Invasive Break Up Time Test (NIBUT) technique with the Bausch & Lomb keratometer. The subject was instructed to rest their

chin on the designated chin rest and align their forehead with the headrest. Initially, the subject blinked several times and then refrained from blinking. Time was measured from the last blink until the appearance of any distortion or break in the "mires." This time interval was recorded as the NIBUT measurement. If the subject blinked during the measurement, the test was paused briefly, and resumed after a few blinks. A one to two-minute break was provided between each measurement. Three readings were taken, and the average of these readings was utilized for subsequent statistical analysis (Mohidin et al., 2002).

c) Corneal Coloring Assessment (Efron Grading Scale)

The evaluation of corneal staining will involve using the Efron Grading Scale to assess any marks or damage on the subject's cornea before applying contact lenses. Initially, fluorescein dye will be applied to the subject's eyes using fluorescein strips moistened with saline solution. The subject will be instructed to look up, and the moistened fluorescein strip will be gently touched to the lower eyelid, followed by blinking. Using a biomicroscopic slit lamp equipped with a blue cobalt light, any staining or markings on the cornea will be examined. Any observed findings will be documented according to the Efron Grading Scale. Subsequently, the subject's eyes will be rinsed with saline solution to remove the fluorescein dye. The cornea will be divided into five zones (central, superior, inferior, temporal, and nasal) for recording observations, as depicted in Figure 1. The Efron Grading Scale, recognized for its suitability in assessing corneal coloring, will guide the evaluation process (Dundas et al., 2001; Woods & Fonn, 2018).

[figure not shown]

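### The before/after tear tests show change over a day of wear but cannot attribute it to the lens; statements about lenses should rest on the planned between-eye contrasts, and the general objective should say so.

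*Protocol*

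**What the plan says.** The general objective (2.6.1) is causal in wording: "The objective is to examine the impact of FDA contact lenses Group I, II, III, IV, and silicone hydrogel on tear assessment". The hypothesis (2.4) is about change over time: "there was no significant disparity observed in tear assessment, corneal staining, and comfort levels before and after one day (8 hours". The research question (2.3) and the specific objectives (2.6.2) are also mostly framed as before versus after 8 hours.

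Section 3.1.9 describes three wearing sessions: groups I and II, then III and IV, then Va and Vb. On allocation it says "Each lens will be placed on one eye only", and for the first session group I goes on one eye "while group II FDA contact lenses will be positioned on the opposite side, with the positioning being randomized and unknown to the subjects". The second and third appointments repeat the procedure, including the examination before insertion. The two-week rest periods contain no tear measurement.

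Before insertion, each subject has Schirmer and NIBUT testing and fluorescein staining. For Schirmer, "Three readings will be obtained in millimeters (mm), and the average reading will be calculated for data analysis"; after staining, the "eyes will be rinsed with saline solution to remove the fluorescein dye". Then "These same tests will be conducted after the contact lenses have been worn for 8 hours and subsequently removed".

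Section 3.1.11 plans a paired t-test or Wilcoxon test "to assess the disparities in tear quality and quantity before and after". The end of that sentence is lost in the text available, but 2.3, 2.4 and 2.6.2 make its meaning clear. A further item plans the same kind of test on tear quality and quantity between the two lenses worn in the same session.

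**The concern.** A pre-to-post change in one eye is the sum of whatever the lens did and whatever else changed over those 8 hours. Time of day is one candidate. Another is built into the plan: Schirmer strips, fluorescein and a saline rinse in the morning, followed by the same tests later. Separating the two parts needs a measurement that shares the 8 hours but not the lens, and the design has none.

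Sections 2.6.1 and 3.1.11 do not mention this limit. The same before/after test is implied for each of six lenses, so an ordinary change over the day could be reported as the impact of each of them. The comparison that can support a statement about lenses is already planned, but nothing gives it precedence.

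**Working it through.** **1. Inputs.**
- Sample size from 3.1.4, as printed: 1.96 × 0.3 × 0.7 / 0.0025 = 164.64; 10% of this is 16.46, taken as 16; plus 2 for dropout gives 18. (The printed formula squares Z, and the substitution does not. That is a separate matter and does not affect this point.) I use n = 16 completers and n = 18.
- Test: paired t-test or Wilcoxon (3.1.11). A two-sided 5% level is assumed.
- Size of any non-lens 8-hour change: not given. I assume 0.25, 0.5 and 0.75 SD of the within-eye change.

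**2. What each comparison estimates.** Let m be the non-lens change shared by both eyes, L_A and L_B the effects of the two lenses in a session, and e the error.
- Before/after in eye A: change = m + L_A + e_A. Its mean is m + L_A, and the design holds nothing that estimates m alone.
- Between eyes, same session: (m + L_A + e_A) − (m + L_B + e_B) = (L_A − L_B) + (e_A − e_B). The shared m cancels. The same holds for post-wear values, because random placement makes the expected pre-wear eye difference zero.

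**3. Chance that the before/after test is significant when L_A = 0.** With d = m/SD, the statistic is noncentral t with n − 1 df and noncentrality d√n. For n = 16 the critical value is 2.131.

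| d | d√16 | n = 16 | n = 18 |
|---|---|---|---|
| 0 | 0 | 5.0% | 5.0% |
| 0.10 | 0.4 | 6.6% | 6.9% |
| 0.25 | 1.0 | 15.5% | 17.0% |
| 0.50 | 2.0 | 46.5% | 51.6% |
| 0.75 | 3.0 | 80.1% | 85.0% |

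The Wilcoxon test at n = 16 (4,000 simulated trials, normal changes) gives 4.3% at zero change and 14.7%, 43.4% and 76.6% at 0.25, 0.5 and 0.75 SD.

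**4. Between-eye contrast under a shared change.** Simulation of 40,000 trials per setting, with n = 16 and 18, correlation of the two eyes' changes 0.3, 0.6 and 0.8, and shared change 0 to 0.8 SD, gives a rejection rate of 4.8% to 5.2% throughout.

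**5. Optional adjustment for pre-wear values.** Let r be the correlation between the pre-wear and post-wear between-eye differences (not given). Relative to the unadjusted post-wear contrast, the variance ratio is (1 − r²)(1 + 1/(n − 3)). At n = 16 the second factor is 14/13 = 1.077.
- r = 0: 1.077, about 8% more variance
- r = 0.3: 0.91 × 1.077 = 0.980
- r = 0.5: 0.75 × 1.077 = 0.808
- r = 0.7: 0.51 × 1.077 = 0.549
- Break-even: r = √(1/14) = 0.267

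This assumes bivariate normality. It concerns precision only, since random placement already removes bias.

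**The case against.** The strongest reply is that the paired tests answer the question the protocol mostly asks. The research question, the hypothesis and most of the specific objectives concern before versus after, and a paired test answers that validly. This stands. If tears do drift over 8 hours, the hypothesis in 2.4 is false and rejecting it is correct. The percentages in the table are then power to detect a real change. A reader might infer that the planned tests have an inflated type I error. They do not: at zero change the paired t-test holds 5%. The figures become errors only when the change is credited to the lens.

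A reader might also infer that the protocol commits to drawing lens conclusions from these tests. It does not say so. The mismatch lies between the causal wording of 2.6.1 and a test that cannot deliver it, with no statement of which analysis supports which claim.

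The size of any drift has no anchor in the protocol, and that stands too. At 0.1 SD the rate is only 6.6% at n = 16. The range illustrates the exposure; it does not predict this trial.

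Finally, the between-eye tests are already in 3.1.11, so the request is about priority and labelling. That is true, and it is why the change is cheap. Those contrasts have limits of their own: if both lenses in a pair alter tears equally, they show nothing.

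**Conclusion.** The point holds as a mismatch between objective and analysis, and it should be corrected. That no unworn eye or day is measured is plain from 3.1.9 and does not depend on any assumed number. The before/after tests are sound for change over a wearing day and uninformative about its cause. With an assumed non-lens change of 0.25, 0.5 or 0.75 SD, the chance of a significant result that could be misread as a lens effect is about 16%, 46% or 80% per paired t-test at n = 16. For a change shared by both eyes, the between-eye contrast stays at 5%.

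Two conditions apply to relying on those contrasts. Random eye placement is explicit for groups I and II, and reaches the other pairs through the instruction to repeat the procedure. The contrasts are also relative and confined to the three pairs: the order of the pairs is fixed, so differences across pairs are mixed with session.

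**What to change.** 1. In 3.1.11, report the within-lens before/after tear changes descriptively, as mean change with 95% CI. State that conclusions about lenses rest on the within-session, eye-randomized contrasts I vs II, III vs IV and Va vs Vb.
2. In 2.6.1, reword the general objective to change over a day of wear and relative differences within each lens pair. State that no lens-versus-no-lens effect is estimated; that would need an unworn eye or session.
3. Optional: for each tear outcome and lens pair, regress the between-eye post-wear difference on the between-eye pre-wear difference. Take both differences in the same lens order and leave the predictor uncentred, so that the intercept is the lens difference; report it with a 95% CI. Keep the planned paired t or Wilcoxon test as a sensitivity analysis.

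Items 1 and 2 are wording only, and no result is lost. Item 3 uses data already collected and costs one degree of freedom per contrast. At n = 16 that is at worst about 8% more variance and a CI about 4% wider (r = 0), with a gain in variance once r exceeds about 0.27. Since r is unknown, the sponsor can decline item 3 without weakening items 1 and 2.
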